2 OBJECTIVES

2.1 Primary Objectives

The proposed study has two primary objectives:

- 1. To assess the effectiveness of a bundled pharmacist-delivery strategy consisting of communication and funding strategies on vaccine coverage.
- 2. To determine the increase in pre- and post-intervention knowledge, attitudes, beliefs and behaviours (KABB) of target adults, pharmacists, physicians, and public health practitioners.

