2.2 Secondary Objectives

- 1. To assess the impact of various funding models on vaccination coverage.
- 2. To evaluate a pharmacy-based strategy for recruiting participants for a patient-reported active adverse event following immunization surveillance system.

2.3 Primary Hypothesis:

 Vaccine coverage with all studied vaccines (high dose TIV, meningococcal B vaccine, meningococcal ACWY vaccine, Tdap, herpes zoster vaccine, and travel health vaccines) will increase significantly after implementation of the bundled pharmacist-delivery strategy. A significant increase will be defined as an increase of ≥10% vaccine coverage from preintervention levels.

2.4 Secondary Hypotheses:

- 1. The cost of a vaccine is a key factor in the individual's decision to be vaccinated. It is expected that vaccinations provided at no or minimal charge will have higher uptake than those that require more financial resources to obtain.
- 2. Knowledge about the vaccines studied is low among the general public, but higher among practitioners. There is a high level of support among both the public and health care providers for pharmacists as immunizers. Knowledge and support amongst both providers and the public will increase after implementation of the program.

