Questions to assess the KABB of the public will focus on awareness of vaccines available, attitudes toward vaccines, perceived social pressures to vaccinate, ability to access vaccination, intention to vaccinate, the use of pharmacists as immunizers, willingness to pay for vaccines, and current vaccination status for study vaccines. The health care provider survey will collect information on physicians', nurses' and pharmacists' KABB regarding logistics of vaccine delivery and record keeping, current immunization practices, attitudes toward vaccines, burden of illness associated with vaccine-preventable diseases, pharmacists as immunizers, and the current age restriction (children 5 years of age and older). Educational needs of healthcare providers on the conditions linked to the vaccinations and their prevention will be collected as well.

The public and provider surveys will be distributed accordingly during the 6-month period prior to implementation of the community-wide pharmacy intervention and immediately following the two-year intervention. KABB survey data will be available and collected prior to flu season.

Survey Instruments Development

Validated survey instruments (questionnaires) will be developed using a formative process informed by Ajzen and Timko in the TPB with target constructs from the HBM. Survey instruments will include two different questionnaires and will be distributed twice according to the above timeline:

- 1. The questionnaire for the public contains approximately 50-60 yes or no, or strength of agreement questions using a Likert scale measuring attitudes toward vaccines, perceived social pressures to vaccinate and perceived/actual behavioural controls. More specifically, data collection will include demographic information, perceived susceptibility and severity of illnesses, perceived benefits and barriers to vaccination, intention to vaccinate, educational needs on prevention and protection, use of pharmacists as immunizers and willingness to pay for vaccines. A draft list of questions has been attached; these questions will be modified, reduced in number, and appropriately ordered prior to finalization. The final survey instrument will be resubmitted to the REB for approval.

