- 2. The questionnaire for health care providers will contain approximately 30-40 yes or no, or strength of agreement questions using a Likert scale measuring knowledge, attitudes and beliefs about the logistics of vaccine delivery and record-keeping, current immunization practices, attitudes toward vaccines, burden of illness associated with vaccine-preventable

ROMEO File #: 1021559

diseases, pharmacists as immunizers, and the current age restriction (children 5 years of age and older). A draft list of questions has been attached; these questions will be modified, reduced in number, and appropriately ordered prior to finalization. The final survey instrument will be resubmitted to the REB for approval.

The survey instruments will be constructed following the principles of survey design of Dillman, Smyth, and Christian (2014). Previously validated questions will be employed whenever possible. Statistical analysis will be done with SAS version 9.4 by the Data Management Group at the Canadian Center for Vaccinology (CCfV). Prior to distributing the survey, the content validity of individual questions, as well as the content validity of the entire questionnaire, will be evaluated by a panel of experts comprised of nurses, pharmacists, and infectious diseases physicians and vaccinologists at CCfV. The panel will determine the content relevance of the questions and the questionnaires as a whole using a rating worksheet. Each item will be rated using a standard content validity index with a 4-point ordinal rating scale, where 1 indicated irrelevance and 4 highly relevant. Items that receive a score of 3 or 4 will be judged to have content validity. The content validity index for the entire instrument will be the proportion of items judged to have content validity. Items that do not achieve the required minimum agreement of experts will be eliminated or revised. Test-retest reliability will be assessed by having up to five health care providers and 5 members of the public complete the questionnaires at two different points in time (approximately 14 days apart). A correlation co-efficient will be calculated to compare the two sets of responses; questionnaire responses with a coefficient > 0.70 will be interpreted as consistent.

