6 OUTCOME MEASURES AND STATISTICAL METHODS

6.1 Outcomes/analysis plan/sample size/statistics

6.1.1 Primary Outcomes

- 1. Population specific vaccine coverage before and after bundled pharmacist-delivery intervention.
- 2. Proportion of population in intervention districts whose supplementary health benefit plans cover studied vaccines.
- 3. Public KABB about vaccine preventable diseases and related vaccines before and after program implementation interventions.
- 4. Public willingness to pay and co-pay for studied vaccines.
- 5. Health care KABB regarding pharmacist- delivered vaccine programs.
- 6. Public and health care provider satisfaction with various models of vaccine program delivery.

ROMEO File #: 1021559

Proportions of influenza vaccine recipients who register for CANVAS and who complete the online AEFI survey in intervention versus control communities.

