6.2 Analysis Plan, Statistics and Sample Size

1. KABB Surveys. Although the response rate is expected to be higher, surveys returned from 400 individuals will provide a 95% confidence interval of \pm 5% around the point estimate for any survey question. The first level of analysis will comprise a review of descriptive statistics for trends in the data. The second level of analysis will involve tests of association. Continuous variables will be presented as summary statistics (i.e., mean and standard error) and categorical variables by frequency distributions (i.e., frequency counts, percentages and their two-sided 95% exact binomial confidence intervals). Descriptive statistics will be used to estimate the proportion of respondents who answered correctly the knowledge-based questions and who had specific attitudes towards and beliefs about studied vaccines. Differences in survey responses between groups will be assessed using Fisher's exact tests. For continuous predictors, logistic regression will be used. Overall knowledge scores will be compared using t-tests. Associations between attitude questions, behavioral responses and demographics will be estimated using ordinal logistic regression or Fisher's exact tests. P-values < 0.05 will be considered statistically significant. If the data support further analysis, demographic and population characteristic variables will be used to develop predictive models for knowledge and attitude responses. Logistic regression will be used to predict binary knowledge responses, in which the model is used to predict the probability of agreeing or disagreeing with the associated statement. Ordinal logistic regression will be used to predict ordered attitude responses, where the model is used to assess the degree (strongly disagree, disagree, neither agree nor disagree, agree, strongly agree) to which subjects have knowledge regarding particular issues. The particular ordinal logistic regression model to be fit is a cumulative logit model. For each outcome variable, whether binary or ordered, the collection of demographic and population characteristic variables will be used in a backwards elimination stepwise procedure to develop a multiple regression model. Those predictor variables remaining at the termination of the stepwise procedure are summarized, and p-values are indicated. P-values of <0.05 will be considered statistically significant. If the number of survey respondents $N \ge 400$, then the estimated proportion of the "yes" response to any fixed KABB survey item will have margin of error <.05.

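### Change in knowledge, attitudes, beliefs and behaviours (KABB) is a primary objective, but no measure or contrast decides it and item-level tests at an uncorrected 0.05 carry no exploratory label

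*Combined protocol and SAP*

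**What the plan says.** Section 2.1 gives the second primary objective as: "To determine the increase in pre- and post-intervention knowledge, attitudes, beliefs and behaviours (KABB) of target adults, pharmacists, physicians, and public health practitioners". Section 6.1.1 lists among the primary outcomes "Public KABB about vaccine preventable diseases and related vaccines before and after program implementation interventions" and "Health care KABB regarding pharmacist- delivered vaccine programs". These are domains; neither names an item, a score or a size of change. The expected direction is in section 2.4, under the secondary hypotheses: "Knowledge and support amongst both providers and the public will increase after implementation of the program".

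The instruments are described in section 3.2. For the public: "The questionnaire for the public contains approximately 50-60 yes or no, or strength of agreement questions using a Likert scale". For providers: "The questionnaire for health care providers will contain approximately 30-40 yes or no, or strength of agreement questions using a Likert scale". The public survey also collects demographic information, and both drafts are to be shortened before they are final.

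The analysis is in section 6.2, item 1. A descriptive first level is followed by a second level of association tests. There, "Differences in survey responses between groups will be assessed using Fisher's exact tests"; overall knowledge scores are compared by t-test; and associations involving attitude questions use ordinal logistic regression or Fisher's test. The rule that follows is "P-values < 0.05 will be considered statistically significant". The survey size of 400 rests on the precision of a single proportion.

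**The concern.** The plan cannot say whether its second primary objective was met. The groups being compared could be before versus after, intervention versus control communities, or one respondent type versus another. The overall knowledge score is not marked as deciding, and it does not cover support, attitudes, beliefs or behaviours. If that score and single items disagree, nothing says which prevails. The coverage objective, by contrast, has a 10% criterion (sections 2.3 and 6.2).

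Meanwhile every item that crosses 0.05 may be called statistically significant. If nothing changed, some items may well cross by chance, and nothing in the plan stops them being reported as support for a primary objective. The synopsis says the results will go to public health to inform funding strategies. This point concerns the group comparisons that bear on the objective, not the stepwise predictor models later in the same paragraph.

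**Working it through.** **The plan's own figure.** With 400 respondents and a proportion of 0.5, the 95% margin is 1.96 × √(0.25/400) = 0.049, below 0.05 as section 6.2 states. The figure reproduces. It is the precision of one proportion at one time, and says nothing about error over many before/after tests.

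**Inputs from the documents.** Items: k = 50 to 60 for the public and 30 to 40 for providers, as upper counts (section 3.2). Threshold: 0.05 per test (section 6.2).

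**Assumptions, because the documents are silent.** Tests are two-sided; there is one two-group comparison; each item has a favourable direction; no item truly changes; and all pairs of test statistics share a correlation ρ.

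**Independent items.**
- Any significant difference, 1 − 0.95^k: k = 50 gives 1 − 0.077 = 0.92; k = 60 gives 1 − 0.046 = 0.95.
- A favourable one only, 1 − 0.975^k: k = 50 gives 1 − 0.282 = 0.72; k = 60 gives 1 − 0.219 = 0.78.
- Expected false positives at any correlation: 50 × 0.05 = 2.5 to 60 × 0.05 = 3, half of them favourable.
- Provider questionnaire, favourable only: k = 30 gives 1 − 0.468 = 0.53; k = 40 gives 1 − 0.363 = 0.64.

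**Correlated items.** With Φ and φ the standard normal distribution and density functions, and c = 1.96, the chance of at least one significant difference is

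1 − ∫ [Φ((c − √ρ z)/√(1−ρ)) − Φ((−c − √ρ z)/√(1−ρ))]^k φ(z) dz.

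For a favourable difference only, the second Φ term is dropped. Results for k = 50 to 60:

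| Correlation | Either direction | Favourable only |
|---|---|---|
| 0 | 92-95% | 72-78% |
| 0.3 | 81-85% | 45-48% |
| 0.5 | 62-66% | 32-34% |
| 0.8 | 30-31% | 15-16% |
| Single test | 5% | 2.5% |

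**Conservatism of Fisher's test.** By enumeration, for two equal groups of 200 to 400 (assumed) and true proportions of 0.1 to 0.5, the actual two-sided size at nominal 0.05 is 0.034 to 0.044. Using 0.035 per item, k = 50 to 60 gives:
- either direction: 50-54% at correlation 0.5 and 23-24% at 0.8;
- favourable only: 25-27% at correlation 0.5 and about 12% at 0.8.

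**Fewer outcome items.** If only 40 questions are outcomes, the nominal figures are 87% (independent) and 57% (correlation 0.5) in either direction, and 64% and 29% for a favourable difference.

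**The case against.** Five points can be made for the plan.

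- **Item count.** A reader might infer that each of 80 to 100 items (50 + 30 to 60 + 40) is tested. The documents do not say so. Section 6.2 speaks only of survey responses, the public count includes demographics, the drafts will be reduced, and the two questionnaires go to different people. This stands, and the counts used here are upper bounds.
- **Direction.** A reader might also infer that a chance improvement is likely. The highest percentages count differences in either direction. For a favourable difference, the chance exceeds one half only when items are close to independent; at correlation 0.5 it is about a third. This stands too.
- **Status of the hypothesis.** The expected increase is a secondary hypothesis, and the synopsis words the objective without reference to an increase. That is correct, but sections 2.1 and 6.1.1 still make before/after KABB primary.
- **Descriptive intent.** The first level of analysis is descriptive, 400 is a precision-based size, and nothing says that one significant item establishes the objective. This stands in part. The second level nevertheless adds tests with a significance rule and no exploratory label.
- **A summary measure exists.** The overall knowledge score is planned, but it is not designated as deciding and covers knowledge only.

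**Conclusion.** The concern holds in this form: a primary objective has no designated measure or contrast, and the stated rule inflates false positives if it is followed. For one comparison of 50-60 items with no true change, the chance of at least one favourable significant difference runs from 72-78% (independent items) through 32-34% (correlation 0.5) to 15-16% (correlation 0.8). Allowing for Fisher's test, the low end is about 12%, still well above the nominal 2.5% of a single two-sided test.

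Correlation, sidedness, group size and the number of outcome items are assumptions. Shorter final questionnaires lower the figures. Repeating the tests over more contrasts, professions or communities raises them. The documents do not support saying that 80 to 100 items are each tested or that a false improvement is more likely than not; the point needs neither. It should be corrected, but it calls for changes to the analysis text, not to the survey design.

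**What to change.** In section 6.2, item 1:

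1. State the contrast that decides the KABB hypothesis. One example is after versus before in intervention communities relative to control communities for the public, and after versus before for providers. If the public contrast is relative to controls, the analysis must estimate a difference between two changes, which a plain two-group t-test does not do.
2. Designate two deciding measures, each in the public and in providers: the overall knowledge score already planned, and one pre-named measure of support for pharmacists as immunizers. That makes four tests, with Holm's procedure at overall two-sided 0.05.
3. Label all other item-level, profession-level and community-level comparisons exploratory. Report them with estimates and 95% confidence intervals, and do not apply the 0.05 significance rule to them.
4. Say when the measures were chosen if survey data have already been seen. The protocol is dated 18 May 2021 and its influenza surveillance seasons are 2016-17 and 2017-18, so this is possible, although the documents do not say. If the choice came after the data were seen, label all KABB tests exploratory.

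The cost is wording, with no new data or respondents. The downside is a stricter threshold for the named measures (0.05/4 = 0.0125 for the smallest p-value), and single-item differences can no longer be claimed as confirmed. Attitudes, beliefs and behaviours outside the support measure would become exploratory, a narrowing the sponsor should accept openly or meet by naming a further measure.

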Vaccine coverage (number vaccinated divided by the number eligible for vaccine) will be measured using pharmacy database analysis, public health vaccine reports by physicians, vaccine doses delivered (in all four regions), and by public survey within the study communities (part of the KABB survey). Statistics Canada census data from 2015 will be used to determine the denominator for those eligible for the vaccine by 5-year age groups.

3. Adverse Events Following Immunization Reporting (AEFI)

Using the Canadian National Vaccine Safety Network (CANVAS)'s surveillance system for adverse events following seasonal influenza vaccination, we will compare the proportions of eligible individuals who register for CANVAS and complete the online AEFI survey among pharmacies using active recruitment strategies (e.g., handing out information sheets and registration forms) and those using passive recruitment strategies (e.g., displaying posters and information sheets).

Sample Size
 There are four communities involved in the study, Saint John and Moncton, New Brunswick and New Glasgow/Pictou/Antigonish and Kentville/Wolfville/New Minas, Nova Scotia. All participating pharmacies in each community will be allocated either to the bundled pharmacist-delivery intervention or to standard care (control arm). Residents in each community will receive a KABB survey, regardless of whether or not they were vaccinated as part of this study. Information and registration forms

ROMEO File #: 1021559

for CANVAS surveillance will be actively distributed to those who received influenza vaccines in the intervention communities and information on CANVAS will be displayed at pharmacies in control communities. A sample size of 400 for the KABB survey will provide a margin of error of less than 5% for estimated proportions. For vaccine coverage, a separate sample size of 596 per group will provide power of at least 80% to detect superiority.

Endpoints Outcomes/analysis plan/sample size/statistics Outcomes

- 1. Population-specific vaccine coverage before and after programimplementation interventions.
- 2. Proportion of population in intervention districts whose supplementary health benefit plans cover studied vaccines.
- 3. Public KABB about vaccine-preventable diseases and related vaccines before and after program-implementation interventions.
- 4. Public willingness to pay and co-pay for studied vaccines.
- 5. Healthcare providers KABB regarding pharmacist- delivered vaccine programs.

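### Fisher's exact test is the only test named for group differences on the KABB surveys' five-level Likert items, so the hypothesised increase has no order-respecting test

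*Combined protocol and SAP*

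**What the plan says.** Section 6.2, item 1 assigns one test to group comparisons: "Differences in survey responses between groups will be assessed using Fisher's exact tests". Logistic regression follows for continuous predictors and t-tests for overall knowledge scores. The threshold is "P-values < 0.05 will be considered statistically significant"; sidedness is not stated.

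The items are of mixed type. Section 3.2 gives the public questionnaire "approximately 50-60 yes or no, or strength of agreement questions using a Likert scale". The provider questionnaire also has "strength of agreement questions using a Likert scale measuring knowledge, attitudes and beliefs about the logistics" of vaccine delivery, among other topics. Section 6.2 lists the five ordered answers, from strong disagreement to strong agreement.

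Ordinal methods do appear in 6.2, in two places. One is associations among attitudes, behaviours and demographics, where ordinal logistic regression or Fisher's test may be used, with no rule for choosing. The other is predictive models, to be built only if the data allow, of which it says "The particular ordinal logistic regression model to be fit is a cumulative logit model". The predictors named for those models are demographic and population characteristics. Neither survey wave nor study arm is among them.

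KABB change is primary objective 2, and section 2.1 words it as an increase. The explicit hypothesis is item 2 under Secondary Hypotheses (section 2.4): "Knowledge and support amongst both providers and the public will increase after implementation of the program".

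**The concern.** The comparisons that bear on objective 2 are before against after and intervention against control. For a Likert item, the only test the plan names for these is Fisher's.

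On a 2 x 5 table, Fisher's test (in the Freeman-Halton extension) gives the same p-value if the five columns are shuffled. A significant result says that the distributions differ, not that agreement rose, and no effect estimate is attached to it. The plan does not say whether items would instead be collapsed to agree/not agree. That would restore a direction but treat strong and mild agreement as the same answer.

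At stake is the chance of missing a real general shift in attitudes. A null KABB result might then reflect the choice of test rather than the programme.

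**Working it through.** **The plan's own figure.** The synopsis says "A sample size of 400 for the KABB survey will provide a margin of error of less than 5% for estimated proportions". The half-width at a proportion of 0.5 is 1.96 × √(0.25/400) = 0.049, so the figure reproduces. It concerns the precision of one proportion. The documents give no power or effect size for any KABB comparison, and do not say whether 400 is per group, per community or per wave.

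**Assumptions for the power check.** Five-level item; two-sided 0.05; independent respondents; equal groups of 100, 200 or 400; proportional-odds shift. None of these effect sizes, response shapes or group sizes comes from the plan. The ordered test is the tie-corrected Wilcoxon test, which is the score-test analogue of the cumulative logit model.

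**Analytic check.** The noncentrality giving 80% power on 1 degree of freedom is 7.85. The same noncentrality on the 4 degrees of freedom of an unordered 2 x 5 table gives 59.5%, a loss of about 20 points. Ordered power of 50%, 70%, 90% and 95% corresponds to 31%, 48%, 74% and 84%. The loss is largest in the middle of the power range and shrinks towards its ends.

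**Simulation.** 1000 trials per scenario (Monte Carlo error about 1.5 points per estimate), with 30%, 40% or 65% agreeing at baseline. Power in %, gain in percentage points:

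| Per group | Odds ratio | Ordered | 2 x 5 Fisher | 2 x 2 Fisher | Gain over 2 x 5 | Gain over 2 x 2 |
|---|---|---|---|---|---|---|
| 200 | 1.25 | 23–25 | 13–15 | 14–16 | 10 | 8–10 |
| 200 | 1.5 | 60–62 | 39–40 | 44–47 | 20–23 | 14–19 |
| 400 | 1.25 | 39–41 | 24 | 27–32 | 16–17 | 9–13 |
| 400 | 1.4 | 73–78 | 52–57 | 59–64 | 21–24 | 14–17 |
| 400 | 1.5 | 87–90 | 70 | 74–78 | 17–20 | 12–14 |
| 400 | 1.75 (30% and 40% only) | 99–100 | 95–96 | 96–97 | 4 | 3 |

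Runs on four further response shapes (25% to 70% agreeing) bring the ranges for odds ratio 1.25 to 1.5 and 200 to 400 per group to roughly 9–24 points over 2 x 5 Fisher and 6–23 over 2 x 2 Fisher. With 80% agreeing at baseline, 200 per group and odds ratio 1.5, the gain over 2 x 2 Fisher was larger: 56.9 − 27.0 = 29.9 points. At 100 per group, the gain over 2 x 5 Fisher was 3–7 points for odds ratio 1.25–1.3 and 19–23 for 1.75–2. Under no effect, rejection rates were about 4–6% for the ordered and 2 x 5 tests and about 3–5% for 2 x 2 Fisher, so a little of the gain over the latter is its conservatism.

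**A case that goes the other way.** Take baseline probabilities (0.10, 0.15, 0.25, 0.30, 0.20) and move 10 points from neutral to agree only, giving (0.10, 0.15, 0.15, 0.40, 0.20). Agreement goes from 50% to 60%, an odds ratio of (0.6/0.4)/(0.5/0.5) = 1.5 on the collapsed item. With 400 per group, power is about 29% ordered, 90% unordered and 79% for 2 x 2 Fisher. Under a proportional-odds shift with the same 50% to 60% change, the figures are 88.7%, 74.0% and 79.2%. The collapsed test cannot tell the two patterns apart; the ordered test does well on one and badly on the other.

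**The case against.** The strongest reply has four parts.

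- **Fisher's test is valid.** This stands. The point is efficiency and fit to the hypothesis, not type I error.
- **Section 6.2 is framed in proportions, so an agree/not agree table is a natural reading.** This partly stands. A reader might infer that the plan can show no direction at all; the documents do not support that. A collapsed table has a direction, and the planned percentages with exact 95% intervals show one descriptively. But the plan does not say that items will be collapsed, and collapsing still costs power under a general shift.
- **Ordinal regression is already planned for attitude responses.** True, but not for this contrast. A reader might infer either that the plan neglects ordinal methods or that it has covered the point; the text supports neither.
- **The best test depends on the shift expected.** This stands in full. Undecided people coming to agree is an increase in support, and an information campaign could plausibly produce it. In the example above the ordered test loses about 61 points to the unordered test (90 − 29) and 50 to the collapsed one (79 − 29). The ordered test is therefore not uniformly better, and its weakness has to be stated.

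**Conclusion.** The point holds as a gap in specification with a cheap improvement available. For Likert items, the before/after and intervention/control comparisons have no order-respecting test, although objective 2 and the section 2.4 hypothesis speak of an increase.

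The size is conditional. The gains of roughly 9–24 points (over 2 x 5) and 6–23 points (over 2 x 2) need a proportional-odds shift, odds ratio 1.25 to 1.5 and 200 to 400 per group. At 400 per group and odds ratio 1.7 to 2, the gain over 2 x 5 is 0–6 points. A reader might take a loss of some 15 to 24 points as a property of this plan. The documents do not support that, because they state no KABB effect size, response distribution or group size.

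Nor is the whole of objective 2 affected. Yes/no items suit Fisher's test and overall knowledge scores go to t-tests. The share of Likert items is unknown, since section 3.2 describes the question lists as drafts. The hypothesis of increase is itself listed as secondary.

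**What to change.** In section 6.2, item 1:

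- Limit Fisher's exact test to yes/no and nominal items.
- For Likert items, assess group differences with the cumulative logit model already named, with survey wave and/or study arm as predictor. Report a common odds ratio with its 95% confidence interval and a check of the proportional-odds assumption.
- Keep the agree proportion and its exact interval for each group as a stated descriptive companion to every Likert comparison.
- State the limitation: the ordered test is much less sensitive to a shift confined to neighbouring categories, which can also be an increase in support. This is why the agree proportion must be reported alongside.

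The cost is a few sentences and little programming, as the model and SAS are already in the plan. No further data or respondents are needed. The price in power is the limitation just described.

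### KABB predictors are selected by backward elimination and then judged at 0.05 in the same data, so their p-values, effects and intervals are distorted; multiplicity across items is a separate problem.

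*Combined protocol and SAP*

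**What the plan says.** Section 6.2, item 1 (KABB Surveys), describes the survey analysis in stages: descriptive statistics, then tests of association, then modelling. The modelling is conditional: "If the data support further analysis, demographic and population characteristic variables will be used to develop predictive models for knowledge and attitude responses". Binary items get logistic regression and ordered items a cumulative logit model. For each outcome the candidate variables "will be used in a backwards elimination stepwise procedure to develop a multiple regression model".

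On reporting, the plan says: "Those predictor variables remaining at the termination of the stepwise procedure are summarized, and p-values are indicated". The next sentence sets the threshold: "P-values of <0.05 will be considered statistically significant".

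The section gives no list or number of candidate variables, no significance level for staying in the model, no multiplicity adjustment and no internal validation.

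On the number of items, Section 3.2 (Survey Instruments Development) says: "The questionnaire for the public contains approximately 50-60 yes or no, or strength of agreement questions". It adds that "data collection will include demographic information", and of the draft items that "these questions will be modified, reduced in number, and appropriately ordered prior to finalization". The provider questionnaire is put at about 30-40 questions.

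Section 2.1 makes KABB change the second primary objective, and Section 6.1.1 lists public and provider KABB among the primary outcomes.

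**The concern.** A variable survives backward elimination because its p-value is small. Reporting that p-value against 0.05 treats the variable as if it had been named in advance. If the stay level is itself 0.05, every survivor is significant by construction and the final test adds nothing.

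Selection also favours estimates that happen to be large in this sample. Retained odds ratios are therefore pushed away from 1, and their intervals, calculated as if no selection had taken place, miss the truth too often. When predictors are correlated, as demographic variables usually are, dropping a truly related variable can shift its effect onto an unrelated one.

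Section 3.2 expects the survey's findings on barriers and facilitators to guide later interventions, and Section 8.2 takes results to decision makers. A list of significant predictors made up partly of chance findings, with inflated effects, could misdirect that work. The vaccine coverage objective is not affected.

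**Working it through.** **The plan's own figure.** The only numerical design figure for the KABB surveys is the margin of error at 400 respondents: 1.96 × √(0.25/400) = 0.049. This reproduces the stated margin of under 5%. It concerns the precision of one proportion and has no bearing on the models.

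**Inputs from the documents.** Backward elimination per outcome, threshold 0.05, 400 respondents, and a public questionnaire of about 50-60 questions.

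**Inputs that are assumed.** The number of candidates per model (k), the stay level (0.05), the true effects and the correlation between predictors. The documents give none of these.

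**Step 1: does elimination itself raise the false count?** With no true associations and independent predictors at n=400, simulated false predictors per model were:

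| Candidates | Full model | After elimination |
|---|---|---|
| 8 | 0.39 | 0.38 |
| 12 | 0.62 | 0.60 |

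Theory for the full model gives 8 × 0.05 = 0.40 and 12 × 0.05 = 0.60. In this setting elimination adds nothing, and the count is ordinary multiplicity.

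**Step 2: what does elimination distort?** The setting is n=400, 8 to 12 candidates, three weak true effects (log odds ratio 0.15), the rest null, and correlation 0 to 0.5.

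- Nominal 95% intervals for retained predictors covered about 40-72%. Part of this is built in: a null predictor retained at 0.05 has an interval that excludes zero. The rest comes from exaggerated true effects.
- Retained effects averaged about 0.27-0.34 on the log odds scale. 0.27/0.15 = 1.8 and 0.34/0.15 = 2.3, so about twice the truth.
- With predictors correlated at 0.3-0.5, false predictors rose by about 20-70% over the full model.
- A prespecified full model, with all its coefficients reported, kept 95% coverage.

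**Step 3: multiplicity, a separate matter.** If every candidate is null, the expected number of chance predictors is items × k × 0.05. The last column is simulated.

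| k | 50 items | 60 items | Elimination, correlation 0.3, 50 and 60 items |
|---|---|---|---|
| 5 | 12.5 | 15 | 12.7 and 15.2 |
| 8 | 20 | 24 | 22.5 and 27.0 |
| 10 | 25 | 30 | 28.9 and 34.7 |
| 12 | 30 | 36 | 32.7 and 39.2 |
| 20 | 50 | 60 | 60.2 and 72.2 |

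With 40 modelled items the formula gives 40 × 5 × 0.05 = 10 to 40 × 20 × 0.05 = 40. For one model with 10 null candidates, the chance of at least one false predictor is 1 − 0.95^10 = 0.40.

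**Step 4: how many predictors can a model carry?** For a binary item the limit is set by the rarer response. At an assumed 10% frequency, 400 × 0.10 = 40 events, which is 40/8 = 5 per predictor with 8 predictors and 40/12 = 3.3 with 12.

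**The case against.** The strongest reply is that these models carry little weight. They come after the descriptive and association analyses, are run only if the data allow, are called predictive, and are not the pre/post comparison behind the KABB objective. Item proportions already get exact 95% intervals, and overall knowledge scores are already compared by t-test. This stands as a limit on the consequence. It does not rescue the method: the condition for modelling has no criterion, and a prediction aim would call for validation or performance measures, whereas the plan reports p-values.

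A second reply is that elimination does not cause the number of chance findings, and that a full model would not reduce it for independent predictors. Step 1 shows that this is right. A reader might infer that elimination will yield some 19 to 35 false predictors. The documents do not support that reading. It needs about 19/(50 × 0.05) = 7.6 to 35/(60 × 0.05) = 11.7 candidates per model, every questionnaire item modelled, and no true association anywhere. Yet no candidate list is given, only knowledge and attitude responses are modelled, and the item list is to be shortened. In the other direction, the count leaves out the provider survey and the second survey round.

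A reader might also infer a 92-95% chance of at least one false positive from the item comparisons alone (1 − 0.95^50 and 1 − 0.95^60). That requires independent items and tests of exactly 5%. Fisher's exact test, which the plan names, is conservative: with an actual size of about 0.034-0.044 (assuming 200-400 per group and response rates of 10-50%), the figure is 82-93%. Items from one questionnaire are also unlikely to be independent.

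**Conclusion.** The point holds as a defect of method with a modest consequence. Selecting and testing predictors in the same data makes the reported p-values too small, the effects too large and the intervals too narrow. The sizes in Step 2 (coverage of about 40-72%, effects about doubled, false predictors up by about 20-70% when predictors are correlated) rest on assumed weak effects, candidate counts, correlations and stay level. Stronger effects or more respondents would reduce the distortion.

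The multiplicity across items is real but distinct. The range of about 12 to 60 chance predictors depends on an assumed 5 to 20 null candidates and on treating the approximate total questionnaire length as the number of modelled outcomes. It is an illustration and not a forecast.

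Neither part undermines the coverage analysis, and the documents do not support reading this as a failure of the pre/post KABB comparison.

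**What to change.** In Section 6.2, replace backward elimination with one full model per modelled item. Prespecify the list of demographic variables and size it to the number of respondents giving the rarer response. Report all odds ratios with 95% intervals, whether or not they reach 0.05; picking out only the significant ones would bring the selection bias back.

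Label item-level and predictor results as descriptive, and name the overall knowledge score comparison, which is already planned, as the main knowledge result. This labelling is what deals with the multiplicity, since the full model alone does not remove it.

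The change is to analysis wording and needs no new data. It costs larger tables, slightly wider intervals and fewer results called significant.
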